13.1. Quality Control

1) Requirements for Participating Personnel

Personnel participating in the clinical trial should have corresponding professional expertise, qualifications, and research capabilities. They must carefully study and discuss the clinical research protocol and trial manual, and be selected after qualification review. The personnel should remain relatively stable. Qualified personnel are required for the management of archives, drug or device usage, and calibration of relevant testing instruments.

To ensure that all surgical procedures are performed by neurointerventionalists with a certain level of experience, the operators of interventional surgeries must meet the following requirements: Operators should have more than 3 years of experience in cerebrovascular interventional therapy and have independently completed at least 30 stent-like thrombectomy surgeries.

2) Training of Participating Personnel

Through pre-clinical trial training, participating personnel should fully understand and recognize the clinical trial protocol and the specific connotations of its indicators. The description of subjective symptoms should be objective, without inducement or suggestion. The prescribed objective indicators should be examined according to the time, location, and method specified in the protocol. Attention should be paid to observing adverse reactions, and follow-up observations should be conducted.

3) Quality Control Measures for Laboratories

Unified experimental testing indicators, standard operating procedures, and quality control programs should be established. The criteria for abnormal laboratory test results should be based on the normal reference ranges of each center. Special test items must be conducted by dedicated personnel.

13.2. Quality Assurance

1) Establishment of a Multi-center Coordination Committee

The Central Trial Coordination Committee consists of the principal investigators and key researchers from each clinical trial unit. The Coordination Committee is responsible for the implementation of the entire trial and addressing issues related to the trial.

2) Data and Safety Monitoring Board (DSMB)

This study establishes a Data and Safety Monitoring Board (DSMB) responsible for providing recommendations on whether to terminate or continue the trial during the execution phase. The DSMB members consist of experienced neurologists, neurointerventionalists, and statisticians who are not involved in the execution of the clinical trial. The DSMB is formed by the DSMB chair and operates according to the DSMB charter. A data report will be conducted after every 100 eligible patients have completed follow-up, and adverse events will be reported to the DSMB chair under strict confidentiality measures. Based on the analysis results, the DSMB will provide recommendations to the principal investigator on continuing the trial, modifying the trial protocol, or suspending the trial.

The DSMB will carefully review all clinical and safety endpoint events.

This study does not establish a stopping endpoint for safety events.

3) Imaging Core Laboratory

The Imaging Core Laboratory is composed of expert committee members: Professors [name], [name], and [name]. Two experts will independently evaluate all imaging data from patients, and the third expert will make the final decision in case of disagreement. All patients' imaging data will be uploaded via storage media and the internet and evaluated by the Imaging Core Laboratory. The evaluation content of the Imaging Core Laboratory includes: ①Baseline and 12-hour CT-based ASPECTS score; ②Baseline CTA/MRA/DSA assessment of vascular occlusion and postoperative DSA vascular recanalization; ③CT-based evaluation of SICH and aSICH within 48 hours.

Additionally, before patient enrollment, CT/CTA and other imaging interpretations will be evaluated by at least two neurointerventional or radiology physicians arranged by each sub-center, and the evaluating physicians will not be directly involved in the trial execution.

14. Ethical Requirements

14.1. Development, Revision, and Ethical Review of the Study Protocol

The clinical trial protocol shall be finalized and signed by the principal investigators after joint discussion and revision before the start of the clinical trial. It shall be implemented after being approved by the Chinese Registered Clinical Trial Ethics Review Committee.

If any issues arise during the actual implementation of the clinical trial that require revisions to the protocol, such revisions must be discussed by the Coordination Committee and made by the lead unit. The revised protocol shall be submitted again to the Chinese Registered Clinical Trial Ethics Review Committee for approval and record-keeping before implementation.

14.2. Patient Informed Consent

Before the start of the clinical trial, the investigator must provide detailed information about the clinical trial to the patient or their legally authorized representative (guardian), including the nature of the trial, its purpose, potential benefits and risks, alternative treatment options available, and the patient's rights and obligations as stipulated in the Declaration of Helsinki. This ensures that the patient or their representative is fully informed and aware of their right to withdraw from the study at any time. The clinical trial can only begin after the patient or their legally authorized representative (guardian) has expressed consent and signed the Informed Consent Form. The Informed Consent Form shall be kept as one of the original documents of the clinical trial for future reference.

Contact information must be collected from every patient, and the doctor should provide their own contact information to the patient, to ensure that the investigator can be reached in case of any changes in the patient's condition. This also facilitates the investigator's ability to stay informed about changes in the patient's condition.

To protect patient privacy, patient names should not appear on the Yiducloud Scientific Research Collaboration Platform. Investigators should confirm patient identity and make records using patient codes.

15. Patient Recruitment and Management System

15.1. Patient Recruitment

When a patient arrives at the hospital's emergency department or outpatient clinic, a neurologist or relevant specialist will inquire about the patient's medical history, conduct a physical examination, and make an initial diagnosis of acute ischemic stroke in the anterior circulation. Imaging examinations such as head CT/CTA/MRA/DSA will be performed to further confirm the diagnosis of acute large artery occlusive stroke in the anterior circulation. The patient will then be assessed against the inclusion and exclusion criteria to determine eligibility. While discussing the patient's condition with the patient and/or their family members, they will be informed about the basic details of the clinical trial (title, purpose, basic process, significance, etc.) and the associated risks. The patient and/or their family members will be asked if they wish to participate in the trial. If they agree, a written informed consent form will be signed, and the patient will be randomized into a group by the lead unit investigator through an app. If they decline, treatment will be provided according to the patient's and/or their family's preferences.

15.2. Patient Management System

- Investigators will promptly collect personal information such as the patient's name, ID number, home address, and contact details, as well as data on current medical history, past medical history, and auxiliary examination results.
- 2) When signing the informed consent form, investigators will fully inform patients about the trial and respect their right to decide, either voluntarily or after discussing with family members, whether to participate in the trial.
- 3) Arrange patient follow-ups during the trial and strictly complete all examinations as specified in the protocol.
- 4) Educate patients that if they need to undergo other examinations or treatments due to comorbidities, they should inform the investigator promptly or during the next follow-up. Investigators should record relevant information timely after being informed.
- 5) Inform patients about possible adverse reactions that may occur during the study. Advise patients to promptly notify the investigator of any physical discomfort experienced during the trial, and the investigator will determine the appropriate management plan.
- 6) Inform patients that their study data will be kept confidential by the research team and request that they not disclose any trial-related information to external sources.

16. Trial Schedule

	Start date	End date
Preparation Stage	2024-02-01	2024-07-31
Implementation Stage	2024-08-01	2025-07-31
Follow-up and Data Collection	2025-08-01	2025-10-31
Data Compilation and Analysis	2025-11-01	2025-11-30
Summary	2025-12-01	2025-12-31

17. Data Management and Data Traceability Regulations

17.1. Case Report Form (CRF) Completion and Transfer

The CRF shall be completed by the investigator for each selected case in a timely manner. After review by the monitor, the first copy of the completed CRF shall be transferred to the data manager for data entry and management. No changes shall be made to the content of the CRF after the transfer of the first copy.

17.2. Data Entry and Modification

The data manager shall use the Yiducloud Scientific Research Collaboration Platform to develop a data entry program for data entry and management. To ensure data accuracy, two data entry clerks shall independently perform double entry and proofreading.

For any questions regarding the CRF, the data manager will send a Query Form (QF) to the investigator, and contact them through the monitor for a prompt response. The data manager will make data modifications, confirmations, and entries based on the investigator's responses. If necessary, additional QFs may be issued until correct confirmation is obtained.

17.3. Requirements for Investigators to Fill Out Clinical Trial Records

- 1) For all patients who have signed the informed consent form and been screened as eligible, detailed medical records and eCRFs on the Yiducloud Scientific Research Collaboration Platform must be carefully completed. All items must be filled in, with no blanks or omissions (see filling instructions).
- Original laboratory test reports, urine pregnancy test reports, CT reports, etc., must be complete and attached to the original medical records. All these documents require the signatures and dates of the clinicians and investigators participating in the clinical trial. The data recorded in the eCRF on the Yiducloud Scientific Research Collaboration Platform must be accurately checked against the medical records and original test reports.
- 3) The original medical records (inpatient medical records) serve as the primary source of information. Any corrections can only be made by drawing a line through the incorrect information, noting the corrected data alongside, and providing a reason. These corrections must be signed and dated by the clinicians and investigators participating in the clinical trial. No erasure or covering of original records is allowed.
- 4) Data that is significantly higher than expected or outside the clinically acceptable range must be verified, and a necessary explanation must be provided by the clinician participating in the clinical trial.

During the trial, clinical records shall be completed by investigators at each sub-center in paper-based CRFs, accurately documenting the condition and treatment of each patient.

17.4. Inspection of Data Records by the Inspector

If an inspector is assigned to this trial, the following requirements shall be met:

- 1) The inspector shall regularly check the informed consent forms of patients and the screening and inclusion of cases during the trial;
- 2) Confirm that the content of the eCRF on the Yiducloud scientific research collaboration platform is filled in correctly and consistent with the original data;
- 3) Changes in treatment, concomitant medications, comorbid diseases, loss to follow-up, and missed examinations for each patient shall be confirmed and recorded; reasons for withdrawal and loss to follow-up of hospitalized patients shall be verified and explained;
- 4) Confirm that all adverse events are recorded, and SAEs are reported within the specified time and recorded;
- 5) Verify that the trial devices and medications are supplied, stored, and used in accordance with relevant regulations, and make corresponding records;
- 6) When checking the original medical records, attention should be paid to ensure that the records are timely, accurate, authentic, standardized, and complete, especially:
- a) The consistency of the informed consent time and screening number sequence recorded in Version 2.0 27 Release date: July 23, 2024

- the original medical records;
- b) The observation and examination items and records should be consistent with the eCRF on the Yiducloud scientific research collaboration platform;
- Check whether the judgment of the severity of the disease, efficacy evaluation, and safety evaluation are correct;
- d) The patient's name, communication address, and hospitalization number on the medical record must be filled in and ensure their authenticity.

17.5. Database Locking

After the data is reviewed and the established database is confirmed to be correct, the data management personnel, principal investigators, statistical analysts, sponsors, and inspectors shall jointly review the data, complete the final definition and judgment of the analysis population, and then the database shall be locked by the data administrator.

The locked database or files generally cannot be modified.

18. Data Preservation and Trial Summary

18.1. Data Preservation

To ensure evaluation and supervision by the National Medical Products Administration, researchers should agree to preserve all research data according to the requirements of the "Good Clinical Practice (GCP)", including confirmation of all participating patients (able to effectively cross-check different records such as original hospital records and laboratory test reports), all original signed patient informed consent forms, etc., for a period of 5 years after the termination of the clinical trial.

All data from this clinical trial belongs to the First Affiliated Hospital of Fujian Medical University.

Unless required by the National Medical Products Administration, researchers shall not provide any data to third parties in any form without the written consent of the First Affiliated Hospital of Fujian Medical University.

18.2. Trial Summary

After the completion of the trial, the Department of Biostatistics of Fujian Medical University will be responsible for establishing a clinical data database and conducting unified data processing. The statistical analysts will perform statistical analysis on the data from each participating unit separately and on the combined data from all units. The statistical results of each participating unit will be summarized in a brief format, which will be confirmed by each unit and used as the basis for writing the "Clinical Trial Summary Report". The completed summary report, after being stamped, will be submitted to the Department of Neurology of the First Affiliated Hospital of Fujian Medical University for archiving. The Department of Neurology of the First Affiliated Hospital of Fujian Medical University will be responsible for completing the "Clinical Trial Final Report".

The final report of the trial shall be publicly published only after agreement from all participating units. No party shall unilaterally publish the report without the consent of the other party.

19. Composition of Functional Institutions for Clinical Trials

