Proportion of patients with pneumonia. 1) Inclusion Criteria Age 18 years; 2) The time from onset to randomization was within 12 hours; 3) Anterior circulation ischemic stroke was preliminarily determined according to clinical symptoms or imaging examination: 4) Occlusion of the intracranial internal carotid artery, the M1- or M2-segment of the middle cerebral artery confirmed by CT angiography (CTA), MR angiography (MRA), or digital subtraction angiography (DSA); Baseline National Institutes of Health Stroke Scale (NIHSS)>6; 5) 6) Baseline Alberta Stroke Program Early CT Score (ASPECTS)<6: Planned treatment with endovascular therapy (EVT); Informed consent obtained from patients or their legal representatives. Intracranial hemorrhage confirmed by cranial computed tomography (CT) or **Exclusion Criteria** magnetic resonance imaging (MRI). 2) mRS score ≥ 2 before onset. 3) Pregnant or lactating women. 4) Allergic to contrast agents or glucocorticoids. 5) Participating in other clinical trials. Systolic blood pressure >185 mmHg or diastolic pressure >110 mmHg, and oral antihypertensive drugs cannot control. Genetic or acquired bleeding constitution, lack of anticoagulant factors, or oral anticoagulants and INR > 1.7. 8) Blood sugar < 2.8 mmol/L (50 mg/dl) or > 22.2 mmol/L (400 mg/dl), platelet $< 90 \times 10^{9}/L$. The artery is tortuous so that the thrombectomy device cannot reach the target vessel. 10) Bleeding history (gastrointestinal and urinary tract bleeding) in recent 1 month 11) Chronic hemodialysis and severe renal insufficiency (glomerular filtration rate < 30 ml/min or serum creatinine > 220 umol/L [2.5 mg/ dL]). 12) Life expectancy due to any advanced disease < 6 months. Follow-up is not expected to be completed. 13) Intracranial aneurysm and arteriovenous malformation. 14) Brain tumors with imaging mass effect. 15) Systemic infectious disease. **Treatments** The emergency interventional team is on call 24 hours a day, 7 days a week. Each sub-center selects patients based on the above inclusion and exclusion criteria, and assigns them to either the intravenous methylprednisolone sodium succinate + endovascular treatment group (experimental group) or the placebo (i.e., intravenous methylprednisolone sodium succinate simulator) + endovascular treatment group (control group) in a 1:1 ratio by a web-based APP on mobile phone or computer. Randomization will be stratified by participating centres permutation block size of 8. After patients agree to participate and obtain a random number, they will receive intravenous methylprednisolone sodium succinate or placebo treatment as soon as possible, preferably before the establishment of arterial access and no later than 2 hours after the completion of endovascular treatment. Relevant time points (accurate to the minute) will be recorded truthfully and accurately. The effectiveness and safety of the two treatment regimens will be observed and evaluated.

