4.4. Privacy Protection

completely stored in the hospital where they receive treatment, and laboratory test reports and other examination results will be recorded in the patients' medical records. Only the investigators, ethics committees, and food and drug administration departments of this study will be allowed to access patients' medical records. Any public reports on the results of this study will not disclose the personal identities of patients. We will make every effort to protect the privacy of patients' personal medical information within the limits allowed by law.

According to medical research ethics, apart from personal privacy information, trial data will be available for public inquiry and sharing. Inquiry and sharing will be limited to web-based electronic databases to ensure that no personal privacy information is leaked.

5. Sample Size Calculation

Based on the research results from published literature and combined with clinicians' experience, the 90-day mortality rates for the intravenous methylprednisolone sodium succinate + endovascular treatment group (experimental group) and the placebo + endovascular treatment group (control group) are estimated to be 29% and 38%, respectively. Assuming a 1:1 ratio for the sample sizes of the two groups, a two-sided α of 0.05, and a power of 80%, the estimated sample size is 856 patients. Considering an expected dropout rate of 5%, the maximum estimated sample size, calculated using PASS 15.0, is 902 patients, with 451 patients in each of the intravenous methylprednisolone sodium succinate + endovascular treatment group (experimental group) and the placebo + endovascular treatment group (control group).

6. Randomization

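### Section 18.2 names the centre-confirmed results of each unit, and not the combined analysis, as the basis of the Clinical Trial Summary Report

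*Combined protocol and SAP*

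**What the plan says.** Section 18.2 (Trial Summary) orders two kinds of analysis in one sentence: "The statistical analysts will perform statistical analysis on the data from each participating unit separately and on the combined data from all units". The next sentence concerns the units' results alone. They are put in a short format, "which will be confirmed by each unit and used as the basis for writing the" Clinical Trial Summary Report. The combined analysis is not named as a basis of that report. The section also mentions a separate Clinical Trial Final Report, completed by the lead department, and makes publication of the final report depend on the agreement of all units.

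Three other places bear on this:

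- **Section 5 (Sample Size Calculation)** plans one whole-trial comparison. The 90-day mortality rates "are estimated to be 29% and 38%, respectively", and with "a two-sided α of 0.05, and a power of 80%, the estimated sample size is 856 patients".
- **Synopsis, Treatments:** "Randomization will be stratified by participating centres permutation block size of 8". Section 6.1 describes block randomisation without naming centre.
- **Section 12.3** describes whole-trial intention-to-treat comparisons by chi-square or Fisher's exact test. It lists ten subgroup variables, and centre is not one of them. It gives no centre adjustment, no method or minimum size for centre analyses, and no multiplicity rule.

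**The concern.** Read as written, the Summary Report rests on many small, separate results, each approved by the unit that produced it. No sentence in 18.2 says which result prevails if the units and the combined data point in different directions. The trial has no power to answer its question centre by centre, so chance alone would produce apparent reversals and some apparently significant centres. A report assembled from such results can present noise as differences between centres.

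What the units confirm is also a problem. The text has them confirm statistical results, when what a unit can properly vouch for is that its data are accurate and complete.

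Finally, centre enters the plan where it cannot help (separate analyses) and is absent where it belongs (the combined test, given that randomisation is stratified by centre in the synopsis).

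**Working it through.** **Inputs.** From section 5: mortality 29% v 38%, two-sided alpha 0.05, power 80%, 1:1 allocation, 5% dropout, 856 evaluable and 902 randomised. The number of centres is assumed, because the centre list was removed from the text available. Its absence is not a fault of the plan.

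**1. The plan's own figure.** Unpooled normal approximation:

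n per arm = (1.960 + 0.842)² × (0.38×0.62 + 0.29×0.71) / 0.09² = 7.849 × 0.4415 / 0.0081 = 427.8, so 428 per arm and 856 in total. With dropout, 428/0.95 = 450.5, so 451 per arm and 902 in total. Both stated figures reproduce exactly.

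**2. Power of one centre if 902 patients are split equally over k centres.** With n = 451/k per arm and mean mortality 0.335:

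power = Φ{[0.09 − 1.96√(2×0.335×0.665/n)] / √(0.4415/n)}

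| Centres k | n per arm | Power |
|---|---|---|
| 1 (whole trial) | 451 | 81.8% |
| 2 | 225.5 | 53% |
| 5 | 90.2 | 25% |
| 10 | 45.1 | 14% |

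For k = 2: (0.09 − 1.96×0.04445)/0.04425 = 0.065, and Φ(0.065) = 0.526. At 428 per arm the same formula gives 79.8%.

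**3. Small centres, by exact enumeration.** Deaths in each arm are binomial. Every pair of counts is weighted by its probability, and pairs are summed where the test gives P ≤ 0.05 or where drug deaths exceed placebo deaths. The null case uses 33.5% mortality in both arms. The chance of at least one significant centre is 1 − (1 − a)^k, where a is the null rejection rate per centre.

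| | 50 centres of 18 (9 per arm) | 23 centres of 40 (20 per arm) |
|---|---|---|
| Power per centre, Fisher | 3% | 5% |
| Power per centre, chi-square | 8% | 10% |
| Mortality strictly higher on drug, planned effect true | 25% | 22% |
| The same, counting ties | 44% | 33% |
| At least one centre at P ≤ 0.05, no effect, Fisher | 61% | 45% |
| At least one centre at P ≤ 0.05, no effect, chi-square | 95% | 71% |

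For 50 centres, a = 0.0186 by Fisher, so 1 − 0.9814^50 = 0.61. By chi-square a = 0.0569, so 1 − 0.9431^50 = 0.95. For 23 centres a = 0.0253 and 0.0530, giving 0.45 and 0.71. Both tests are shown because section 12.3 allows either. With so few deaths per arm, Fisher is the more natural choice in centres of this size.

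**The case against.** The strongest reply is that this is a loosely worded reporting clause with no effect on the result. Several readings that go further than the text might be inferred, and the documents do not support them.

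- **That there is no pooled analysis.** There is one, planned in the same sentence as the unit analyses. Sections 5 and 12.3 size and describe only that comparison, and section 12.1.2 ties the analysis to the statistical analysis plan.
- **That a centre result may replace the trial result.** No passage says so. The gap is that 18.2 does not say the combined analysis prevails.
- **That the published report rests on centre results.** The stated link is to the Summary Report, which is archived. The Final Report is separate, and the basis of its conclusion is not stated.
- **That each centre will be tested at 0.05.** Section 18.2 speaks of statistical analysis and a short format, and names no test. The centre-level power and false-positive figures apply only if tests are run.
- **That there are dozens of centres.** The number is unknown here.
- **That units will contest unwelcome results.** This is conjecture. Under section 7.3 the data are locked and analysed under codes A and B, and arms are revealed only when the final report is ready, so units might confirm results that are still coded.

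These points limit the consequence. They do not alter what 18.2 names as the basis of the Summary Report, nor that the units are asked to confirm results. The clause may mean only routine site summaries. If so, one sentence can say it.

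**Conclusion.** The point holds as a gap in the reporting rule. Section 18.2 bases the Summary Report on unit-confirmed unit results, while the rest of the plan supports only a whole-trial comparison, and that comparison ignores the stratum used in randomisation.

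The conclusion that single centres cannot answer the question does not depend on the unknown centre count: no equal split into two or more centres gives more than 53% power. An unusually large centre would do better than the average but would still fall short of the full trial. The other centre-level figures depend on the assumed 50 or 23 equal centres, on the test chosen and, for reversals, on whether ties are counted.

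The sample size of 856 (902 with dropout) stands. The change is worth making because it settles which analysis carries the conclusion and costs almost nothing.

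**What to change.** Amend section 18.2, and carry the same rule into the statistical analysis plan:

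1. Both the Summary Report and the Final Report draw their conclusion from the combined analysis only.
2. That analysis is stratified by or adjusted for centre, as randomised. One example is Mantel-Haenszel by centre, with small centres pooled by a rule fixed before unblinding.
3. Centre results are descriptive: counts by arm, without tests.
4. Units confirm that their data are accurate and complete, before unblinding. They do not confirm statistical results.

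The cost is a few sentences and less analysis work overall. The downside is that centres receive counts instead of test results of their own.
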